8.5 Study Size

This is an estimation study. The study size will depend on the number of reports submitted to the Amgen Global Safety Database for women exposed to Repatha during pregnancy.

8.6 Data Management

As per Amgen's due diligence process, hard copy questionnaire forms are mailed to women exposed to Repatha who have provided consent. Completed forms may be mailed, faxed, or emailed back to Amgen Global Safety (AGS). The forms are processed in the Amgen Global Safety Database in accordance with Amgen policies, processes and practices. Attempts to obtain additional information are performed if consent is provided. If further details are made available to Amgen, the Amgen Global Safety Database is updated.

8.7 Data Analysis

8.7.1 Planned Analyses

8.7.1.1 Interim Analysis/Analyses

Annual interim reports of analyses performed during the study will be submitted to the FDA.

8.7.1.2 Primary Analysis

The primary analysis for both annual reports and final analysis (at the end of the study) describes the approach to summarize primary outcomes.

8.7.2 Planned Method of Analysis

8.7.2.1 General Considerations

The analysis of this exposed case series will be descriptive only.

8.7.2.2 Missing or Incomplete Data and Lost to Follow-up

We are describing pregnancy and infant outcomes among women exposed to Repatha during pregnancy. We are not assessing associations, so missing or incomplete data will not cause bias. However, it may affect the accuracy of our reporting on the description of the population and outcomes. Due to self-report, women with adverse events may be more likely to report than women without. This may result in overestimation of the proportion of exposed pregnancies with adverse outcomes.

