8.7.5.1.3 Selection Bias

Pregnant women exposed to Repatha during pregnancy who consent to share their information with Amgen may be different from those who do not and may affect the accuracy of our estimates as discussed in [section 8.7.2.2](#).

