8.7.5.2 External Validity of Study Design

The findings of this study will be generalizable to any pregnant woman exposed to Repatha.

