8.7.6 Analysis Limitations

None. The study is descriptive.

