8.7.7 Limitations Due to Missing Data and/or Incomplete Data

Some patients may be lost to follow-up resulting in missing data. Patients that are lost to follow-up may differ from those that remain in the study and this could be an issue in this study.

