11.3 Is there a system in place for independent review of study results?				

Comments:

Section 12: Limitations	Yes	No	N/A	Section Number
12.1 Does the protocol discuss the impact on the study results of:				
12.1.1 Selection bias?				
12.1.2 Information bias?				
12.1.3 Residual/unmeasured confounding? (eg, anticipated direction and magnitude of such biases, validation sub-study, use of validation and external data, analytical methods).				
12.2 Does the protocol discuss study feasibility? (eg, study size, anticipated exposure uptake, duration of follow-up in a cohort study, patient recruitment, precision of the estimates)				

Comments:

This is a single arm study so bias and confounding will not impact the results. This is a case series so study feasibility is not applicable.

Section 13: Ethical/data protection issues	Yes	No	N/A	Section Number
13.1 Have requirements of Ethics Committee/ Institutional Review Board been described?				
13.2 Has any outcome of an ethical review procedure been addressed?				
13.3 Have data protection requirements been described?				9.3

Comments:

Cases for this study are drawn from the Amgen Global Safety Database.

Section 14: Amendments and deviations	Yes	No	N/A	Section Number
14.1 Does the protocol include a section to document amendments and deviations?				11.1

Comments:

Section 15: Plans for communication of study results	Yes	No	N/A	Section Number
15.1 Are plans described for communicating study results (eg, to regulatory authorities)?				12

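### The protocol says missing data cannot bias its estimates and that findings apply to any exposed pregnant woman; both statements are wrong for single-arm proportions and conflict with its own text

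*Protocol*

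**What the plan says.** The only objective is to estimate proportions among exposed women and their infants (Section 7.1), with 95% confidence intervals (Section 4 and Section 8.7.2.3.3). Section 8.5 fixes no study size.

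Statements that bias is absent or that the results apply to everyone:

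- Section 8.7.2.2: "We are not assessing associations, so missing or incomplete data will not cause bias".
- Section 8.7.5.2: "The findings of this study will be generalizable to any pregnant woman exposed to Repatha".
- Section 8.7.6, on analysis limitations: "None. The study is descriptive".
- Appendix B, comment to checklist Section 12: "This is a single arm study so bias and confounding will not impact the results". Items 7.2, 7.3 and 12.1 (selection and information bias) are all marked N/A.

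Statements that concede the problem:

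- Section 8.7.2.2, same paragraph: "Due to self-report, women with adverse events may be more likely to report than women without", followed by "This may result in overestimation of the proportion of exposed pregnancies with adverse outcomes".
- Section 8.7.5.1.1: women without complications may be less likely to consent or to stay in follow-up, which alters the denominators. Early spontaneous abortions will not be captured.
- Section 8.7.5.1.3: women who consent "may be different from those who do not and may affect the accuracy of our estimates".
- Section 8.7.7: "Patients that are lost to follow-up may differ from those that remain in the study".

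Sections 8.2 and 8.2.2.1 limit the population to women who consent, and Section 8.4 describes reporting and follow-up as voluntary. Section 8.7.2.4 and all its subsections, including the one on residual confounding and bias, read Not applicable. They give no reason. The checklist comment to Section 10 gives the descriptive nature of the study.

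**The concern.** The argument in Section 8.7.2.2 treats bias as something that can only affect a comparison. An estimated proportion has a target value, the risk among exposed pregnancies, and it misses that target systematically if pregnancies with events are more or less likely to be reported, consented or followed than pregnancies without. Confounding needs a comparison; selection bias and bias from missing outcomes do not.

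Every outcome in this study is a safety endpoint (Section 8.7.3). The study answers an FDA postmarketing requirement (Section 6.2), and its findings may feed into labelling decisions (Section 8.7.2.3.3). A confidence interval reflects sampling error only. With the no-bias sentence and the generalisability sentence left in place, the protocol gives contradictory instructions on how those intervals are to be read and to whom they apply.

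**Working it through.** The protocol gives no sample size, event rate, follow-up rate or precision, so there is no stated figure to reproduce. All numerical inputs below are assumptions, chosen to show direction and scale.

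**1. Is a single-arm proportion protected from bias?** Let the true risk be p, and let pregnancies with the event be R times as likely to enter the analysis as those without (reporting, consent and retention combined). The expected observed proportion is

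pR / (pR + 1 − p),

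which equals p (for p between 0 and 1) only if R = 1.

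| R | true 10% | expected | true 3% | expected |
|---|---|---|---|---|
| 1.5 | 0.150/1.050 | 14.3% | 0.045/1.015 | 4.4% |
| 2 | 0.200/1.100 | 18.2% | 0.060/1.030 | 5.8% |
| 3 | 0.300/1.200 | 25.0% | 0.090/1.060 | 8.5% |

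For a true 10% and n = 100 analysed, the exact (Clopper-Pearson) 95% interval covers the truth with probability 95.6% at R = 1, 74.2% at R = 1.5, 34.0% at R = 2 and 2.1% at R = 3. A larger n does not help: at R = 2, coverage is 57.5% at n = 50 and 10.2% at n = 200.

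**2. Can it go the other way?** Section 8.7.2.3.3 sets the denominator as all exposed pregnant women. If women lost to follow-up remained in it and counted as non-events, the expected proportion would be p × f, where f is the share followed. A true 10% with 70% followed becomes 0.10 × 0.70 = 7%. The protocol does not say that it will count them so; this only shows that the direction is not fixed.

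**3. How much do unknown outcomes leave open?** Take N = 100 identified pregnancies, 70 with known outcome and 10 events.

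- Known outcomes only: 10/70 = 14.3%, exact 95% CI 7.1 to 24.7, a width of 17.6 points.
- All 30 unknown are non-events: 10/100 = 10%.
- All 30 unknown are events: (10 + 30)/100 = 40%.

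The width of the bounds always equals the unknown fraction, here 30 points. At about this risk and N = 100, the bounds overtake the interval at about 17% unknown: with 12/83 known, the CI is 7.7 to 23.9, a width of 16.2 points against 17. The crossover shifts with N.

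**4. Generalisability.** Set side by side, Section 8.7.5.2 covers any exposed pregnant woman; Sections 8.2 and 8.2.2.1 cover only those who consent; Section 8.4 covers only those voluntarily reported; Section 8.7.5.1.1 excludes early losses from measurement; and Section 8.7.5.1.3 says consenters may differ. The first statement cannot stand with the others.

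**The case against.** The best defence is that the protocol discloses the problem. Directly after the disputed sentence it says accuracy may suffer, then names the mechanism and the direction. Three further sections add differential consent, selection by consent and loss to follow-up. A report faithful to those sections would carry the caveats, and nothing in the text says that the confidence interval is the whole uncertainty. The study is also descriptive, with no hypothesis, comparator or decision rule, so correcting the sentences changes no planned point estimate. This much stands: the protocol does not deny the problem throughout, and what is wrong is a false statement set against several true ones. It does not rescue the sentence, because systematic overestimation is bias whatever it is called, and the checklist comment is unqualified.

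A reader might infer that the no-bias and generalisability statements are used to rule out every sensitivity analysis. The documents do not show that. Section 8.7.2.4 gives no reason, the checklist cites only the descriptive nature of the study, and Section 8.7.5.2 is never invoked. The two grounds are related, but no more can be said.

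The proposed bounds also have limits. They cover identified pregnancies with unknown outcome and cannot reach pregnancies never reported, which is the mechanism that Section 8.7.2.2 stresses. Data on non-consenters may be thin, since Section 4 excludes women who refused consent and Section 8.4 stops follow-up without it. Part of the tabulation (non-consent numbers, exposure timing, indication) is already planned in Section 8.7.2.3.3.

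**Conclusion.** The point holds. The statement that missing data will not cause bias is false for an estimated proportion and is contradicted within its own paragraph and in three other sections. The generalisability claim conflicts with the eligibility criteria, the data source and the stated limits on early losses. Section 8.7.6 and checklist items 7.2, 7.3 and 12.1, with their comments, repeat the error. These are affirmative statements in the protocol, not detail that a statistical analysis plan would be expected to supply.

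The size cannot be derived from the documents. Under the assumed inputs, a true 10% is expected to appear as 14.3% to 25.0% when events are 1.5 to 3 times as likely to be observed, and 30 unknown outcomes in 100 leave a range of 10% to 40% around an estimate of 14.3%. Nor do the documents support saying that correction would make the results look worse. The only direction the protocol names is overestimation of harm, which would mean lower true proportions, while the handling of losses could push the other way.

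**What to change.** 1. Section 8.7.2.2: delete the sentence on bias and state that outcome-dependent reporting, consent and loss to follow-up can bias each proportion in either direction.
2. Section 8.7.5.2: replace with a statement that the findings describe voluntarily reported, consenting exposed pregnancies with known outcome, and are not incidence estimates for all exposed pregnancies.
3. Section 8.7.6 and checklist items 7.2, 7.3 and 12.1, with their comments: bring into line with Sections 8.7.5.1.1, 8.7.5.1.3 and 8.7.7.
4. Section 8.7.2.4: replace Not applicable with best-case and worst-case bounds for each primary proportion over identified pregnancies with unknown outcome (all non-events, then all events). Add a comparison of known-outcome and unknown-outcome cases on whatever variables are already held, extending the tabulations in Section 8.7.2.3.3. State that the bounds do not cover pregnancies never reported.

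The cost is wording changes and a small amount of extra tabulation from data already held, with no new data collection. The comparison table will be incomplete where non-consenting women have little recorded, and should say so.

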8.7.2.3 Descriptive Analysis

8.7.2.3.1 Description of Study Enrollment

Descriptive results will be presented in each annual interim report.

8.7.2.3.2 Description of Patient Characteristics

Patients will be pregnant women exposed to Repatha during pregnancy. Demographic characteristics of subjects will be summarized using descriptive statistics. Continuous

variables will be summarized using the mean, standard deviation, median, and range. Categorical variables will be summarized using frequencies and counts.

8.7.2.3.3 Analysis of the Primary, Secondary, and Exploratory Endpoint(s)

All analyses will be descriptive. These cases constitute a case series, thus line listings of pregnancy and maternal complications, pregnancy outcomes, infant outcomes and adverse events will be summarized along with tabulations of the numbers and frequencies of events by category of report: numbers who did not provide consent for follow-up, timing of exposure (first, second, or third trimester), and indication for use of the medication. Collection of exposure and outcome information in this group provides additional evidence on the safety of Repatha use during pregnancy. The denominator is the number of pregnant women exposed to Repatha during pregnancy and the numerator is the number with the outcome.

The proportion of infants with adverse events including complications, medical problems or congenital anomalies at birth will be assessed in infants of women exposed to Repatha during pregnancy with corresponding 95% confidence intervals. The proportion of infants with adverse events at 6 months and 12 months of age will be assessed. All adverse events among mothers who have received Repatha at any time during the pregnancy will be summarized including the proportion with pregnancy and maternal complications. To assess events in the developing fetus and neonate in women exposed to Repatha during pregnancy, the proportion of pregnancies resulting in spontaneous abortions, elective abortions, fetal death/ stillbirths and premature delivery will be presented, along with corresponding 95% confidence.

If the available safety information relevant to exposure during pregnancy represents a safety signal, the signal will be further evaluated through the Amgen safety governance structure and, if deemed necessary, escalated for consideration of changes to the Reference Safety Information (eg, USPI) as well as other forms of risk communication (eg, Dear Healthcare Provider Letters).

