These cases constitute an exposed case series, thus line listings of pregnancy and maternal complications, pregnancy outcomes, infant outcomes and adverse events will be summarized along with tabulations of the numbers and frequencies of events by category of report: numbers who did not provide consent for follow-up, timing of exposure (pre-LMP, which trimester), and indication for use of the medication.

Collection of exposure and outcome information in this group provides additional evidence on the safety of Repatha use during pregnancy. The denominator is the number of pregnant women exposed to Repatha during pregnancy and the numerator is the number with the outcome. The proportion at birth with adverse events including complications, medical problems or congenital anomalies will be estimated in infants of women exposed to Repatha during pregnancy. The proportion of infants with adverse events observed at 6 months and 12 months of age will be estimated. The proportion of mothers who have received Repatha at any time during the pregnancy with pregnancy and maternal complications and adverse events will be summarized. Corresponding 95% confidence intervals will also be presented.

To assess effects on the developing fetus and neonate in women exposed to Repatha during pregnancy, the proportion with spontaneous abortions, elective abortions, fetal deaths/stillbirths and premature delivery will be presented, along with corresponding 95% confidence intervals

If the available safety information relevant to exposure during pregnancy represents a safety signal, the signal will be further evaluated through the Amgen safety governance structure and, if deemed necessary, escalated for consideration of changes to the Reference Safety Information (eg, United States Prescribing Information [USPI]) as well as other forms of risk communication (eg, Dear Healthcare Provider Letters).

5. Amendments and Updates

None.

6. Rationale and Background

In the United States (US), Repatha is indicated: (1) In adults with established cardiovascular disease to reduce the risk of MI, stroke, and coronary revascularization; (2) As an adjunct to diet, alone or in combination with other lipid-lowering therapies (eg, statins, ezetimibe), for the treatment of adults with primary hyperlipidemia (including HeFH) to reduce LDL-C; and (3) as an adjunct to diet and other LDL-C-lowering

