8.3 Variables

8.3.1 Exposure Assessment

The period defining exposure to Repatha during pregnancy will be any number of days, at any dose, and at any time from 90 days prior to the first day of the LMP up to and including the end of pregnancy. Identification of pregnancy will be via postmarketed reporting through Amgen's Global Safety Database.

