8.3.2 Outcome Assessment

Pregnancy outcomes include the number of women reporting pregnancy or maternal complications, as well as, the number reporting:

- Live full-term births
- Spontaneous abortion defined as non-deliberate fetal death which occurs prior to 20 completed weeks post-LMP
- Elective abortion defined as deliberate termination of pregnancy at any time in gestation
- Fetal death/Stillbirth defined as non-deliberate fetal death anytime in gestation at or after 20 completed weeks post-LMP
- Premature delivery defined as live birth prior to 37 weeks gestation as counted from LMP (eg, ultrasound adjusted date or Ballard's score)

Outcomes related to pregnancy and maternal complications will be assessed with a Pregnancy Questionnaire (a sample form included in [Appendix C](#)). Outcomes for live births will be assessed with a Post Due Date Questionnaire (a sample form included in [Appendix D](#)) from the Amgen Global Safety Database.

The number of infants with adverse events including complications, medical problems or congenital anomalies at birth will be assessed with a Post Due Date Questionnaire (a sample form included in [Appendix D](#)) from the Amgen Global Safety Database.

Major malformations or birth defects are defined as abnormalities incompatible with life or requiring medical/ surgical intervention. The term minor birth defect generally refers to minor physical anomalies with less clinical importance that represent deviations from what is considered normal and do not have obvious medical, surgical, or cosmetic consequences. Major birth defects identified up to 1 year of age by the mother or the healthcare provider will be included in the primary analysis. Major structural birth defects may be reported by the mother, a family member or her or her child's HCP via medical records. If a major malformation is reported the medical record will be adjudicated by a physician with expertise in teratology, pediatrics, and dysmorphology. Defects will be

classified using the Center for Disease Controls (CDC) criteria (CDC 2017.:
<https://www.cdc.gov/ncbddd/birthdefects/macdp.html>).

Infant outcomes are the number of cases reporting adverse events at 6 months and 12 months and may include whether they have not followed growth curves or met development milestones as expected for chronological age. These outcomes will be assessed with an Infant Questionnaire (a sample form included in [Appendix E](#)).

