8.7.5 Limitations of the Research Methods

8.7.5.1 Internal Validity of Study Design

8.7.5.1.1 Measurement Error(s)/Misclassification(s)

Identification of pregnant women exposed to Repatha depends upon the accuracy of the incoming information received by Amgen's Global Safety Database. Amgen has a comprehensive system to detect these events and a process to verify the data. However, the postmarket data may have missing information which could lead to not classifying the report as a pregnancy case.

Misclassification of outcomes due to poor patient recall should be reduced in this retrospective and prospective study design. For those women exposed to Repatha during pregnancy that are identified retrospectively, they are likely to accurately recall any maternal complications, pregnancy outcomes, adverse infant outcomes and events that may have occurred. However, exposed pregnant women that do not experience complications or adverse events may be less likely to consent to follow-up or may be lost to follow-up which would affect the denominators for aggregate outcomes.

A limitation of the study design relates to the evaluation of spontaneous abortion rates. Rates of early spontaneous abortion, ie, at 7 to 9 weeks post-LMP or less, will not be measured in a study that enrolls women after recognition of pregnancy. The study results with respect to spontaneous abortion will be limited to cases of late first-trimester and early second-trimester pregnancy loss.

Also, the calculation of frequency of birth defects excludes fetal losses (spontaneous abortions, elective abortions, or fetal deaths) for which no birth defects have been

detected. This may introduce a misclassification bias as there is no uniform evaluation of embryos or fetuses that do not survive. It is unknown what percentage of these pregnancies consists of potentially normal outcomes or structural defects. Amgen Global Safety will attempt to obtain information on structural defects detected at the time of the outcome. However, the malformation status of the aborted fetus may not be known. Therefore, defects reported in these groups will be considered separately from the primary analysis.

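### Pregnancy losses tabulated by trimester of exposure fall from row to row through survival alone, so the planned rows cannot be read against each other

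*Protocol*

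**What the plan says.** Section 8.7.2.3.3 plans line listings and tabulations of numbers and frequencies of events. One classifier is "timing of exposure (first, second, or third trimester), and indication for use of the medication". The abstract (Data Analysis) has the parallel wording "timing of exposure (pre-LMP, which trimester), and indication for use of the medication", which adds a pre-LMP category. The events tabulated include the pregnancy outcomes.

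The one denominator given is general: "The denominator is the number of pregnant women exposed to Repatha during pregnancy and the numerator is the number with the outcome". Section 8.3.1 sets the exposure window as "at any time from 90 days prior to the first day of the LMP up to and including the end of pregnancy", so exposure time stops when the pregnancy stops.

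Section 8.3.2 defines the losses by gestational age: "Spontaneous abortion defined as non-deliberate fetal death which occurs prior to 20 completed weeks post-LMP", and stillbirth as "non-deliberate fetal death anytime in gestation at or after 20 completed weeks post-LMP".

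The only related limitation is in section 8.7.5.1.1: "Rates of early spontaneous abortion, ie, at 7 to 9 weeks post-LMP or less, will not be measured". Section 8.7.6 lists no analysis limitations.

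**The concern.** To be counted as exposed in the second or third trimester, a woman must still have been pregnant then. A woman who meant to continue treatment but miscarried at week 10 can appear only as a first-trimester exposure. The trimester rows therefore differ in how long the pregnancy had already survived, as well as in when the drug was given. Nothing in the protocol conditions a row on gestational age.

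Timing of exposure and indication are the only two clinical splits planned. No test accompanies them, so the rows will be judged by eye. Section 8.7.2.3.3 also sends relevant safety information to signal evaluation and possibly to labelling changes. A steep fall in loss from the first to the third row could be taken as first-trimester harm or as reassurance about late use, when neither is present.

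**Working it through.** The protocol states no loss rate, study size or trimester boundary, so there is no figure to reproduce. The check is first by definition, then by an example with no drug effect.

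**By definition.** Spontaneous abortion ends before 20 completed weeks (8.3.2). Under any usual boundary the third trimester starts later than that, so the third-trimester row must show zero. If the second trimester starts at week 14, its row can hold spontaneous abortions only from weeks 14 to 19. These two statements need no assumed rates.

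**Example with no drug effect.** Assumptions, none from the protocol: 1,000 women, all on drug at LMP; 12% lost in trimester 1 (120); 3% lost from week 14 to before week 20 (30); 20% would continue treatment to the end, independently of outcome; the rest stop in trimester 1.

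*Rows by any exposure (a woman counts in each trimester in which she was exposed):*
- First trimester: (120 + 30)/1000 = 15.0%.
- Second trimester: 200 continuers − 24 lost in trimester 1 = 176; losses 0.2 × 30 = 6; 6/176 = 3.4%.
- Third trimester: 176 − 6 = 170; 0/170 = 0%.

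With 8% + 2% loss the rows are 10.0%, 4/184 = 2.2% and 0%. With 16% + 4% they are 20.0%, 8/168 = 4.8% and 0%.

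If the all-exposed denominator were applied literally to every row, the second row would be 6/1000 = 0.6% and the third 0, so that reading does not remove the fall.

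*Exclusive rows by last exposure, first-trimester row:* the 800 who stop contribute 0.8 × 150 = 120 losses, and the continuers lost in trimester 1 add 24.
- 20% continuing: (120 + 24)/(800 + 24) = 144/824 = 17.5%.
- 50% continuing: (75 + 60)/(500 + 60) = 135/560 = 24.1%.

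Both exceed the true 15.0%.

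**Allowing for missed early losses.** Suppose observation starts at week 8. Let p be the spontaneous abortion risk over weeks 8 to 19, and s the share of it before week 14. Any-exposure rows are then p, p(1 − s)/(1 − ps) and 0. With s = 0.8:

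| p | First | Second | Third |
|---|---|---|---|
| 5% | 5.0% | 0.010/0.96 = 1.0% | 0% |
| 10% | 10.0% | 0.020/0.92 = 2.2% | 0% |
| 15% | 15.0% | 0.030/0.88 = 3.4% | 0% |

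Over these values of p and s from 0.6 to 0.9, the second row runs from 0.5% to 6.6%. The fall remains.

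**Stillbirth.** Assume 0.5% risk spread evenly over weeks 20 to 40 and a third trimester from week 28. The share after week 28 is 12/20, so the third-trimester row shows about 0.6 × 0.5% = 0.3%. It is reduced, not empty.

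**Does conditioning remove the artefact?** In the first example, among pregnancies ongoing at week 14, continuers have 6/176 = 3.4%. Those who had stopped number 800 − 96 = 704, with 0.8 × 30 = 24 losses: 24/704 = 3.4%. The two agree, as they should with no drug effect.

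**The case against.** The best defence is that the study is descriptive. No hypothesis is tested, stratified and subgroup analyses are marked as not applying, and the confidence intervals are attached to the overall proportions. On that view the comparison between trimesters is supplied by the reader. It is true that no formal comparison is planned, and this limits the seriousness. It does not make the rows harmless, because the table invites the comparison and the same section leads on to signal evaluation.

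A second defence is that row rules and table shells belong in a statistical analysis plan. The protocol does leave open whether rows overlap or are exclusive. But it fixes the split by trimester for pregnancy outcomes and gives a denominator with no at-risk condition, and the fall in loss arises under both any-exposure and last-exposure rows.

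A third is that the document already holds the clues: the 20-week cut-off, the statement that observed spontaneous abortions will be late first-trimester and early second-trimester losses, and an index date in section 8.2.5 set at the later of LMP or exposure. A careful reader could work out that the third-trimester zero is definitional. However, section 8.7.2.3.3 does not use the index date in the tabulation, and section 8.7.5.1.1 deals with missed early losses, which is a different problem.

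A reader might infer three stronger things that the documents do not support:
- **That first-trimester exposure is always made to look worse than it is.** With overlapping rows the first row is the true 15.0%. It is inflated only if rows are exclusive by last exposure, which the protocol does not specify.
- **That the same fall is shown for rows by first exposure.** If all women are on drug at LMP, there is only one such row. A gradient would need later starters, about whom the protocol gives nothing.
- **That premature delivery behaves the same way.** Under "Premature delivery defined as live birth prior to 37 weeks gestation as counted from LMP", such births can still follow third-trimester exposure, and the direction can reverse. With 15% loss, 10% of live births preterm and 10% of those before week 28 (all assumed), the first row is 85/1000 = 8.5% and the third is 76.5/841.5 = 9.1%.

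**Conclusion.** The point holds for pregnancy loss. The plain trimester rows condition on survival, so loss frequencies fall across them with no drug effect. The zero for spontaneous abortion in the third-trimester row and the truncated second-trimester row follow from the protocol's own definitions and usual trimester boundaries.

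The percentages rest on the assumed loss rates, trimester boundaries and continuation shares, and are illustrations, not predictions. The overall proportions, not split by trimester, are not affected by this mechanism. The plan should be changed, but this is a fault in one tabulation and does not undermine the study.

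**What to change.** In section 8.7.2.3.3 and the abstract, for spontaneous abortion, elective abortion and stillbirth:
- Do not split first-trimester losses by trimester of exposure.
- For second- and third-trimester exposure, count only losses after the start of that trimester, among pregnancies still ongoing then. Show beside them the pregnancies ongoing at the same gestational age whose exposure had stopped. State the trimester boundaries, and fix exposure status at that gestational age so that later survival does not re-enter the classification.
- Print *not at risk* in place of 0 in impossible cells.

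In sections 8.7.5.1.1 and 8.7.6, state that loss frequencies must not be compared across the plain trimester rows. Keep the plain split for birth defects and infant events among live births.

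The cost is protocol wording and one extra table, with smaller cells. No new data are needed: Appendix C asks for LMP, drug start and stop dates and weeks of use, and Appendices C and D ask for the date and gestational week at which the pregnancy ended.
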